11.2 Accrual Monitoring

Accrual is expected to be rapid given the common use of AIs for adjuvant therapy in postmenopausal women with breast cancer. Allowing for 6 months ramp-up and IRB approval time, accrual of 15 patients/month would allow completion of the study in approximately 2 years. Accrual will be assessed at 1.5 years after study activation. If monthly average accrual in quarters 5-6 after study activation is < 50% of projected accrual, efforts will be made to increase accrual over the succeeding 6 month period. If after 2 years, monthly accrual remains < 50% of projected accrual, study revision will be considered.

11.3 Secondary Endpoints

The following secondary analyses will be conducted:

- a. Multiple linear regression analyses of the individual assessment timepoints will be conducted to identify potential critical effectiveness timepoints and to allow comparisons to other studies. These analyses will include the baseline score (as a covariate) as well as the pre-specified stratification factors.
- b. At weeks 2, 6, and 12, we will investigate whether duloxetine 60 mg daily:
 1. Decreases worst joint pain according to the BPI.
 2. Improves functioning, pain, and stiffness in the knees/hips according to the Western Ontario and McMaster Universities Osteoarthritis (WOMAC) scale. Differences between the two study arms of at least two points on the WOMAC Index are of interest. [\(50, 51\)](#) We will also evaluate clinically meaningful change for the WOMAC Index with respect to the $\frac{1}{3}$ to $\frac{1}{2}$ standard deviation during the study period of 12 weeks.
 3. Improves function, pain and stiffness in the hands according to the Modified Score for the Assessment and Quantification of Chronic Rheumatoid Affections of the Hands (M-SACRAH). Differences between the two study arms of at least two points on the M-SACRAH are of interest. [\(50,51\)](#) We will also evaluate clinically meaningful change for the M-SACRAH with respect to the $\frac{1}{3}$ to $\frac{1}{2}$ standard deviation during the study period of 12 weeks.
 4. Improves functional quality of life as measured by the Functional Assessment of Cancer Therapy-Endocrine Scale (FACT-ES).[\(52,53\)](#) Trial Outcome Index (TOI). Clinically meaningful change in FACT-ES TOI scores will also be based on $\frac{1}{3}$ to $\frac{1}{2}$ of a standard deviation. [\(53-55\)](#)
 5. Improves the proportion of patients reporting changes for the better versus worst as measured by the Global Rating of Change Scale. The GRCs for joint pain and for joint stiffness will be used to identify patients who report they are worse (combining scores of -1 through -3), the same score (score of 0), or better (combining scores of +1 through +3) since the last time they completed the questionnaire. [\(54-56\)](#) Mean scores for the WOMAC Index, BPI, M-SACRAH, and FACT-ES TOI will be compared for groups based on those patients who select “a little better” and “a little worse” on the GRC ratings to identify minimally important change. [\(54-56\)](#)

6. Reduces depression as measured by the Patient Health Questionnaire (PHQ-9). Differences between the two arms of at least five points on the PHQ-9 at 12 weeks will be of interest. (57) Clinically meaningful change in PHQ-9 scores will also be based on $\frac{1}{3}$ to $\frac{1}{2}$ of a standard deviation. (57)
 7. Decreases analgesic use.
 8. Increases adherence to, and reduces the discontinuation rate for, AI therapy.
 9. Affects measures of pain interference.
 10. Reasons for treatment discontinuation will also be described.
- c. Interaction tests between treatment and stratification variables will be conducted to explore whether these factors are predictive of average pain scores.
 - d. A logistic regression analysis of responders will be conducted, where a response to intervention is defined as a reduction of 2 or more points in average pain according to the BPI. (50)
 - e. In addition, we will explore the relationship between the severity of arthralgias and degree of benefit from therapy in each of the treatment groups and inherited variants in genes responsible for duloxetine metabolism and activity (COMT, HTR3A, SLC6A2, SLC6A4, CYP1A2, CYP2D6) and aromatase (CYP19A1). Finally, we will explore the relationship between baseline and change in serum inflammatory cytokine levels with 12 weeks of treatment and the degree of benefit from therapy in each of the treatment groups.

For linear scales, secondary endpoints will be analyzed using multiple linear regression analyses including the baseline score as a covariate and the pre-specified stratification factors. For binary outcomes, logistic regression will be used.

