No effective pharmacologic therapy has yet been identified for management of these symptoms, as many patients do not experience relief of symptoms with analgesic therapy. The current treatment for AIMSS is limited to oral analgesics and exercise. Neither has optimal effect, and long term use of oral analgesics is problematic. Six weeks of acupuncture therapy has been shown to be beneficial compared to sham acupuncture, but long-term benefit of this treatment is unclear. (6)

Investigators at the University of Michigan recently conducted a Phase II open-label clinical trial of duloxetine in 35 postmenopausal women who had been treated with AI therapy for at least 2 weeks and who developed new or worsening pain after starting AI therapy (details below). This definitive multi-institutional randomized, placebo-controlled Phase III trial is founded upon the positive results of the pilot study.

Duloxetine.

Duloxetine is a selective serotonin- and norepinephrine-reuptake inhibitor (SNRI) which is FDA-approved for the treatment of major depressive disorder (MDD), diabetic peripheral neuropathic pain, generalized anxiety disorder, fibromyalgia, and chronic musculoskeletal pain, including osteoarthritis (OA) and low back pain. (7-14) Small uncontrolled studies have also demonstrated that it is potentially effective for treatment of menopausal symptoms and sleep disturbances. (17,18)

Multiple duloxetine doses and schedules have been studied in these various clinical scenarios. (10,11,13,22) In general, duloxetine 60 mg daily was effective and relatively well tolerated in the majority of trials. Some studies demonstrated improved tolerability with a dose-escalation rather than initiation of treatment at the effective dose. Improvement in pain control occurred rapidly in all studies, which typically demonstrated a partial response within 1 to 2 weeks and near maximal response within 6 weeks. In studies of patients with fibromyalgia, the improvement in BPI average pain score was independent of the presence of major depressive disorder.

A small study demonstrated a possible effect of duloxetine therapy on menopause-related symptoms in women with depression. (18) In the 14 postmenopausal patients with MDD who completed the study, improvement was noted in vasomotor, sleep, and anxiety symptoms. Overall pain and pain interference also improved significantly compared to baseline.

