11.0 STATISTICAL CONSIDERATIONS

11.1 Primary Objective

Joint pain will be assessed using “average pain” according to the BPI-SF. Enrollees must currently be taking AIs and must exhibit joint pain with a minimum BPI-SF average pain score of 4; scores of 4 to 10 are considered to reflect moderate to severe pain. (42) Patients will be stratified at randomization by the use of average baseline pain according to the BPI (4-6 vs 7-10) and prior taxane use (yes vs. no). The primary assessment time of 12 weeks, upon which power calculations are based, corresponds to completion of the intervention and allows cross-trial comparisons to be made with **S0927**, which is evaluating a different pharmacologic agent for treatment of AIMSS in the same patient population.

This study stipulates an $\alpha=0.05$ two-sided test, with an estimated 5% non-adherence (reducing the nominal effect size) and 15% dropout rate (increasing the total required sample size) at 12 weeks after randomization. (16, 43) In addition, the design will

incorporate a 10% contamination rate (which also reduces the nominal effect size) based on the assumption that a portion of the patients will not benefit from intervention based on joint pain with a different etiology that is not associated with AI treatment (this has a similar impact on power calculations as a “drop-in” rate).[\(44\)](#)

The proposed sample size incorporates adjustments for loss, non-adherence, and contamination. The power for the design will be a function of the difference detected and the standard deviation at 12 weeks after randomization.

Difference Detected: Although a difference of 2 points in the BPI has been identified as representing a clinically meaningful *individual* level difference, for power calculations assessing group-level differences, we will test a smaller effect. [\(45\)](#) Specifically, an incremental difference in pain reduction due to duloxetine over placebo of about 1.0 points at 12 weeks has been repeatedly found in the setting of fibromyalgia. [\(43,46\)](#)

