Standard Deviation: Multiple studies of AI-induced joint pain have found the standard deviation for BPI “average pain” at follow-up on placebo to be about 2.0 to 2.5 points. [\(47,8\)](#) The design assumes a common standard deviation between arms; a similar standard deviation has been observed in a pilot study of duloxetine. [\(16\)](#) We assume a SD of 2.3 points at 12 weeks for this study (the estimated average SD found in Arnold, Clin J Pain, 2009). [\(8\)](#)

For a 1.0 point difference and a 2.3 point SD at 12 weeks, with other parameters as specified above, 270 eligible patients would be required for 80% power under a two-arm normal design. Power will be higher with lower observed standard deviation or a larger observed difference.

The following considerations clarify the impacts of loss, non-adherence, and contamination on the sample size calculations:

- A two-arm normal design with $\alpha=0.05$ two-sided test and a 2.3 point SD to detect a difference of 1.0 points requires approximately 166 patients (83 per arm) for 80% power.
- An estimated 5% non-adherence and 10% contamination both reduce the nominal effect size, from 1.0 points to 0.85 points. This increases the required sample size to 230 total patients (115 per arm).
- To account for an estimated 15% dropout rate, the total required sample size must be further increased by 15%, as in $230/0.85 = 270$ total patients.

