The primary analysis will rely on longitudinal measures of BPI at Weeks 2, 6, and 12 for improved power. (Thus the proportion of patients with zero follow-up observations will likely be less than the specified 5% non-adherence and 15% dropout at 12 weeks used for power calculations.) Assessment windows of +/- 7 days, +/- 14 days, and +/- 14 days will be allowed for the 2, 6, and 12 week timepoints. (Given the primary analysis is based on longitudinal measures, a sensitivity analysis will consider all observations within 14 weeks of registration.) The analysis will be performed using mixed models, adjusted for baseline average pain and the stratification factors. To minimize missed assessments, SWOG utilizes an electronic system to remind institutions in real-time that patients are due for follow-up assessment. If the proportion of missing follow-up data is >20% (the sum of the specified targets for non-adherence and dropout), plots of mean pain levels over time for patients grouped by number of follow-up responses will be examined to check for patterns of informative missing data. Should these plots suggest that data may not be missing at random, pattern mixture models, which models missingness patterns through stratification, will be utilized for analysis of the longitudinal BPI pain data. [\(48, 49\)](#)

Under the intention-to-treat principle, the primary analysis will be based on all eligible, randomized patients. To allow for an ineligibility rate of 8%, as found on our recent Symptom Control study [S0715](#), a total of 294 patients will be enrolled to achieve 270 eligible patients.

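### Section 11.3a looks for critical effectiveness timepoints with a separate regression at each visit, but no planned analysis compares the treatment effect between visits

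*Combined protocol and SAP*

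**What the plan says.** Section 11.3, item a, plans this: "Multiple linear regression analyses of the individual assessment timepoints will be conducted to identify potential critical effectiveness timepoints". A second stated purpose is comparison with other studies. On the model terms it says: "These analyses will include the baseline score (as a covariate) as well as the pre-specified stratification factors".

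Two other places could have supplied a comparison between visits, and neither does.

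- **Primary analysis, Section 11.1.** It uses all three visits ("The primary analysis will rely on longitudinal measures of BPI at Weeks 2, 6, and 12 for improved power"), and the model is described in one sentence: "The analysis will be performed using mixed models, adjusted for baseline average pain and the stratification factors". No treatment-by-visit term and no contrast between visits is stated.
- **Interaction tests, Section 11.3, item c.** "Interaction tests between treatment and stratification variables will be conducted". These concern baseline pain group and prior taxane use, not visit.

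The plan does not define a critical timepoint, and it states no null hypothesis for item a.

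**The concern.** A model fitted to one visit has no time dimension. Its treatment coefficient can be compared with zero at that visit, but it cannot show that the effect at Week 6 differs from the effect at Week 2 or Week 12. Three separate fits also give no standard error for such a difference. The same patients contribute correlated scores, the separate fits do not estimate that covariance, and the set of responders may change from visit to visit.

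Item a therefore poses a question about timing without a method that compares times. Because no rule is given, an analyst or reader is left to look at which visits reach significance, or which estimate is largest. The first treats a difference in significance as a difference in effect. The second names a critical visit every time, even when the effect is constant. At stake is a secondary statement about onset or loss of benefit, for example that the drug works by Week 6 but not at Week 12.

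**Working it through.** **Inputs from Section 11.1:** two-sided α 0.05, power 80%, SD 2.3 (stated for 12 weeks), effect 1.0 point diluted to 0.85, 115 per arm evaluable, 15% dropout, 8% ineligibility.

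**Assumed, because the documents are silent:** SD 2.3 at Weeks 2 and 6 as well; the same true effect at all three visits; between-visit correlation ρ; baseline-to-follow-up correlation r; critical read as significant at 0.05.

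**1. Reproduce the plan's figures.** n per arm = 2(1.960 + 0.842)² × SD² / effect².
- At 1.0 point: 83.04, so 83 to 84 per arm (plan: 83).
- At 0.85 points: 83.04 / 0.7225 = 114.9, so 115 per arm (plan: 115).
- 230 / 0.85 = 270.6 (plan: 270), and 270 / 0.92 = 293.5, so 294 (plan: 294).

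The design reproduces to rounding.

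**2. Power at one visit, unadjusted.** SE = 2.3 × √(2/115) = 0.303. Mean z = 0.85 / 0.303 = 2.80. Power = Φ(2.80 − 1.96) = 0.80.

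**3. How often the three tests disagree, unadjusted.** P(disagree) = 1 − P(all three significant) − P(none significant), from a trivariate normal with mean 2.80 and correlation ρ.

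| ρ | all three | none | disagree |
|---|---|---|---|
| 0.3 | 0.570 | 0.029 | 0.401 |
| 0.5 | 0.612 | 0.050 | 0.338 |
| 0.7 | 0.659 | 0.080 | 0.261 |
| 0.9 | 0.722 | 0.128 | 0.150 |

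Weeks 6 and 12 alone disagree in 17–23% for ρ 0.7–0.5.

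**4. The same with the baseline adjustment that item a plans.** Residual SD = 2.3√(1 − r²). Residual correlation = (ρ − r²)/(1 − r²).

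| r | ρ | residual SD | residual correlation | power per visit | disagree |
|---|---|---|---|---|---|
| 0.3 | 0.5 | 2.194 | 0.451 | 0.836 | 0.310 |
| 0.3 | 0.7 | 2.194 | 0.670 | 0.836 | 0.240 |
| 0.5 | 0.5 | 1.992 | 0.333 | 0.899 | 0.232 |
| 0.5 | 0.7 | 1.992 | 0.600 | 0.899 | 0.184 |

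Patient-level simulation of the actual regressions (20,000 trials per row, t tests, complete data) gives 0.321, 0.243, 0.242 and 0.193 in the same order. Hence roughly 19–31%.

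**5. Sensitivity, unadjusted.** For ρ 0.7–0.5:
- true effect 0.5: 36–47%
- true effect 1.0: 15–19%
- SD 2.0: 16–21%
- SD 2.5: 31–41%

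With all 135 per arm analysed, 12–31% for ρ 0.9–0.3.

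**6. The direct comparison.** In the same constant-effect settings, a 2-df treatment-by-visit test rejects in 5%. Its power when timing does matter follows from a noncentral chi-square with λ = Σ(effect − mean effect)² / [SE²(1 − ρ)]. Baseline adjustment leaves SE²(1 − ρ) unchanged. For effects of 0.30, 0.85 and 0.85 the sum of squares is 0.2017.
- ρ = 0.5: λ = 0.2017 / 0.0460 = 4.38, power 0.45.
- ρ = 0.7: λ = 0.2017 / 0.0276 = 7.31, power 0.68.

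That is about 45–70% for a Week 2 effect 0.55 points smaller. For a difference of exactly 0.50 points the same formula gives 38–59%.

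**The case against.** Item a can be read more modestly, as asking at which visits there is evidence of benefit. Per-visit regressions answer that. The analysis is secondary, it is worded as finding potential timepoints, and its other purpose is well served by per-visit estimates. All of this stands, and it limits the weight of the point. It does not turn tests against zero into a comparison of visits, should such a comparison be drawn.

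Three stronger readings are tempting, and the documents do not support them.

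- **That the plan will call a visit critical because its p-value is below 0.05 and another's is not.** Section 11.3 states no such rule and no null of equal effects. The disagreement figures are conditional on that reading.
- **That an error rate of 5% is inflated to 19–31%.** Each planned test keeps its 5% rate against zero effect at its own visit. Disagreement arises because power per visit is about 80–90%, so one visit of three often misses. The 5% for the treatment-by-visit test describes a different test, one that the plan does not contain.
- **That Section 2.0 shows an error in item a.** It reports that earlier studies "typically demonstrated a partial response within 1 to 2 weeks and near maximal response within 6 weeks". This is background on other populations and does not contradict Section 11.3. If anything, it makes an exactly constant effect from Week 2 less likely, so the constant-effect case is a benchmark and not a forecast.

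The numbers are also soft. Neither correlation is in the documents, SD 2.3 is given only for 12 weeks, and earlier visits may have more than 115 per arm.

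**Conclusion.** The point holds as a gap in method for a secondary aim: item a seeks critical timepoints, and nothing planned compares visits. If visits were singled out by significance, a constant 0.85-point effect would give a mixed pattern in roughly 19–31% of trials. That rests on SD 2.3 and 115 per arm at every visit, between-visit correlation 0.5–0.7 and baseline correlation 0.3–0.5. Without baseline adjustment the figure is 26–34%, or 15–40% for between-visit correlation 0.9–0.3. It measures limited power per visit. The point is a cheap improvement, not a flaw in the main result, and it leaves the primary test, the sample size and the use of per-visit estimates for cross-study comparison untouched.

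**What to change.** Add one or two sentences to Section 11.3a:

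- Report the per-visit estimates with 95% confidence intervals, for description and comparison with other studies.
- Base any statement about critical timepoints on one repeated-measures model of Weeks 2, 6 and 12: a 2-df treatment-by-visit test, then the differences in treatment effect for Week 6 minus Week 2 and Week 12 minus Week 6, each with a 95% interval.
- State that significance at one visit and not at another is not evidence that the visits differ.

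The cost is one extra model on data already collected; a longitudinal mixed model of the same visits is planned anyway. The downside is the limited power shown above. Fewer timing statements will be made, and the text should say that a non-significant treatment-by-visit test does not establish a constant effect. The contrast intervals show how much remains uncertain.

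### Section 11.3 b.5 collapses the seven-point Global Rating of Change to worse, same and better and names no model; a seven-level proportional-odds model would use the grading already collected.

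*Combined protocol and SAP*

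**What the plan says.** The GRC is objective g under section 1.3, Additional Exploratory Objectives. Its analysis is in section 11.3 b.5, at weeks 2, 6 and 12, for joint pain and for joint stiffness. The comparison is whether duloxetine "Improves the proportion of patients reporting changes for the better versus worst as measured by the Global Rating of Change Scale". The seven scores become three groups. The text identifies "patients who report they are worse (combining scores of -1 through -3), the same score (score of 0") and, as the third group, better (+1 to +3).

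No model is named for this comparison. The closing paragraph of 11.3 gives two general rules. Linear scales get multiple linear regression with the baseline score and the stratification factors. For the rest, "For binary outcomes, logistic regression will be used". Section 11.3 contains no ordinal model and does not say how *same* enters a better-versus-worse contrast. The *a little better* and *a little worse* answers are used separately, but only to estimate minimally important change on the other scales.

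**The concern.** Two things are lost or left open.

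- **The grading.** Once +1, +2 and +3 are one group, a drug that moves patients from slightly to much better shows no benefit on this measure. The plan treats the grades as informative when it estimates minimally important change, but not when it compares the arms.
- **The place of *same*.** The plan defines three groups but states a two-sided contrast. Leaving out patients who answer *same* selects on an answer given after randomisation. Merging them with either side gives a different comparison. Two ratings at three visits make six comparisons that depend on a choice not yet written down.

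At stake is the sensitivity and clarity of one patient-reported exploratory measure, not the trial's main result.

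**Working it through.** **1. The plan's own figures (section 11.1).** The plan states "This study stipulates an $\alpha=0.05$ two-sided test, with an estimated 5% non-adherence". With n per arm = 2 × (1.960 + 0.842)² × SD² / difference² and SD 2.3:

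- Difference 1.0: n = 83.0 per arm. The plan states 83 (166 in total); exact power at 83 is 79.98%.
- Non-adherence and contamination "reduce the nominal effect size, from 1.0 points to 0.85 points". Difference 0.85: n = 114.9, so 115 per arm and 230 in total, as stated.
- Dropout: 230/0.85 = 270.6 (stated 270). Ineligibility: 270/0.92 = 293.5 (stated 294).

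These reproduce, but they concern average pain. No power is claimed for the GRC.

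**2. Inputs for the GRC check.**

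- From the plan: 115 evaluable per arm, two-sided 0.05.
- Assumed: a latent normal shift of 0.85/2.3 = 0.37 SD, borrowed from average pain.
- Assumed: five placebo distributions over -3 to +3, in per cent:
  - A: 3, 7, 15, 25, 25, 17, 8
  - B: 2, 5, 10, 23, 30, 20, 10
  - C: 2, 5, 13, 45, 20, 10, 5
  - D: 1, 3, 6, 15, 30, 28, 17
  - E: 5, 10, 20, 30, 20, 10, 5

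**3. Formulas.** Cut-points are the normal quantiles of the placebo distribution, and the duloxetine arm is shifted against them.

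- Ordinal: tie-corrected Wilcoxon test, close to the proportional-odds test. Power = Φ[(|θ − ½| − 1.96√v₀)/√v₁], where θ = P(Y>X) + ½P(Y=X), v₀ = (2/n)(1 − Σp̄³)/12, and v₁ is the variance of the estimated θ under the alternative.
- Binary: two-proportion normal test.

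*Example, E, better versus not better.* Placebo 0.350. The cut-point is 0.385, and 0.385 − 0.370 = 0.016 after rounding, so duloxetine is 0.494. The difference is 0.144. The null standard error is √(0.422 × 0.578 × 2/115) = 0.0651 and the alternative one is 0.0644. Power = Φ[(0.144 − 0.1277)/0.0644] = 60%.

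**4. Results at 0.37 SD, unadjusted.**

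| Placebo worse/same/better (%) | Seven-level ordinal | Three-level ordinal | Better vs not better | Better vs worse, *same* dropped |
|---|---|---|---|---|
| A: 25/25/50 | 76% | 65% | 60% | 61% |
| B: 17/23/60 | 76% | 61% | 57% | 51% |
| C: 20/45/35 | 75% | 69% | 60% | 63% |
| D: 10/15/75 | 75% | 50% | 49% | 36% |
| E: 35/30/35 | 76% | 69% | 60% | 68% |

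Four of these (A to D) were checked with 400 simulated trials each, using fitted models. Seven-level proportional odds gave 71-79%, logistic better versus not better 50-60%, and logistic better versus worse 33-63%.

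**5. Other shifts.**

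| Shift | Seven-level ordinal | Collapsed, all three kinds |
|---|---|---|
| 0.435 SD (1.0/2.3) | 87-88% | 45-82% |
| 0.25 SD | 43-44% | 20-39% |
| 0.10 SD | 11% | 8-10% |

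The ordering holds at each shift. At 0.10 SD the gain is only about 1 to 4 points.

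**6. Why a small shift is plausible later.** Section 15.2a has patients rate change since they last filled out the questionnaire. After the first follow-up, that is change since the previous visit. Section 2.0 expects near-maximal pain response within 6 weeks. In its Table 1, pilot mean average pain was 5.5 at baseline and 2.5, 2.1, 2.3 and 2.1 at weeks 2, 4, 6 and 8. Most of the fall came before week 2, so little difference between arms may remain to be rated at weeks 6 and 12.

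**The case against.** The strongest reply is that the plan says less than a critic might read into it.

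- **Binary logistic regression and loss of *same*.** A reader might infer that the GRC will be cut to two groups, with *same* dropped or merged, and fitted by logistic regression. The documents do not say so. The logistic sentence is general and does not mention the GRC. *Same* is kept as its own group, and comparing all three proportions between arms fits the text. The conditioning problem arises only if *same* is dropped. This stands. What survives is that the model and the role of *same* are unstated, and that even a three-group ordinal comparison reaches only 50-69%, because the collapse itself loses information.
- **Different question.** The stated objective is a proportion better versus worse. A common odds ratio over seven levels answers something related but different, and adds an assumption. This partly stands, and is why the proportions should still be reported.
- **Size.** No GRC distribution or effect is in the documents, and the shift comes from another measure. This stands: the loss is a range under assumptions.
- **Covariates.** A reader might infer that the logistic models, including the responder model in 11.3d, are unadjusted. The plan is only silent, which is missing detail. The power gain shown here comes from keeping seven levels, since the check is unadjusted.

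**Conclusion.** The point holds as a cheap improvement to an exploratory endpoint. The plan reduces the GRC to three groups, states a better-versus-worse contrast and names no model. Any collapsed comparison gives up the grading.

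Under the five assumed distributions, 115 per arm and a 0.37 SD shift, the seven-level analysis has about 75% power, against 36-69% for the collapsed ones. The loss runs from about 6 points (C, three-level ordinal) to 39 points (D, better versus worse). It depends on the distribution and on how *same* is treated.

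A reader might infer that a loss of this size applies at every visit. The documents do not support that: the recall period runs from the last questionnaire, and near a 0.10 SD shift the difference is about 1 to 4 points. Nor does the point touch the sample size, the primary analysis or the primary conclusion.

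**What to change.** In section 11.3 b.5, state that the arms are compared on the seven-level GRC, for joint pain and for joint stiffness, with a proportional-odds model giving a common odds ratio. Include every patient with a rating, so that *same* is one level of the outcome. Adjust for baseline average pain and the stratification factors; the GRC has no baseline value of its own. Report worse, same and better percentages by arm beside the odds ratio, which keeps the stated objective visible.

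The cost is wording only: all seven levels are already collected, and no visit, form or sample size changes. There are two drawbacks. The proportional-odds assumption must be checked, across all six cut-points and not only the two that separate the three groups. And a common odds ratio is less direct to read than a proportion.
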